In this study, we are investigating the neural mechanisms *causally* involved in how people navigate through their immediately visible environment (e.g., walking around one's bedroom flawlessly and effortlessly, not bumping into the walls or furniture). To investigate whether particular neural mechanisms are *causally* involved in "visually-guided navigation", we use repetitive transcranial magnetic stimulation (rTMS) to temporarily disrupt the functioning of particular brain regions in healthy adults while we show them simple visual stimuli of places (e.g., bedrooms, kitchens, and living rooms) and ask them to perform simple computer tasks (e.g., imagine they are walking through the room, and respond via button press whether they can leave through a door on the left, center, or right wall, as indicated by a continuous path on the floor), or ask them to complete simple behavioral tasks (e.g., actually walk around a small room and search for hidden objects).

3. Background

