The use of rTMS to investigate the causal involvement of particular brain regions in particular human abilities (as proposed here for the causal involvement of OPA in visually-guided navigation, in particular) is not novel. Several studies (Pitcher et al., 2007; Pitcher et al., 2008; Pitcher et al., 2009; Sadeh et al., 2011; Pitcher et al., 2012; Solomon et al., 2013; Pitcher, 2014; Pitcher et al., 2014) have used it to investigate face recognition, two studies ([name] et al., 2013; Ganaden et al., 2013) have used it to investigate scene recognition (i.e., our ability to recognize, not navigate through, a bedroom, for example), and yet two other studies (Rafique et al., 2015; Mullin et al., 2013) have used it to investigate object recognition. In all of these studies, the disruption of face, scene, or object recognition occurred between ~50 to 150 ms after a briefly flashed stimulus, and after that all processing returned to normal. This brief temporal window of disruption demonstrates that the effects of rTMS on visual cortex are very transient (see Bolognini & Ro, 2010 and Wassermann, 1998 for reviews), and no permanent disruption of function has ever been reported. After the experiment, participants will remain under supervision for about 15 minutes, verbally confirm they feel safe to leave (after the 15 minutes), and then will be escorted to the exit.

4. Study Endpoints

The general question for this research is to determine, using rTMS, the *causal* involvement of OPA in visually-guided navigation, using two tasks (a simple computer-based task and a simple behavioral task,

described above in the Abstract, and again just below). Given this question then, we propose to test the following two specific hypotheses:

Experiments involving the simple computer-based task (e.g., imagine you are walking through the room, and respond via button press whether they can leave through a door on the left, center, or right wall, as indicated by a continuous path on the floor)

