i) If OPA is causally involved in visual scene navigation, then disruption of this region, using rTMS, will lead to a decrement in performance on the "visually-guided navigation task" (i.e., imagine you are walking through the room, and respond via button press whether they can leave through a door on the left, center, or right wall, as indicated by a continuous path on the floor), but not on the "scene categorization task" (i.e., imagine you are standing in the pictured room, and respond whether you are in a bedroom, kitchen, or living room) – the control *condition*.

Primary outcome measure: To determine baseline performance, we will also apply rTMS to a control site (i.e., the vertex – a bit of the brain at the very top of the head, not implicated in visually-guided navigation, and identified as the direct midpoint between the bridge of the nose and the inion, and between the participants' temples), and predict a decrement in performance on the visually-guided navigation task, only after rTMS is applied to OPA (but not vertex). There are no secondary outcome measures.

Experiments involving the simple behavioral task (i.e., actually walk around a small room and search for hidden objects).

ii) If OPA is causally involved in visually-guided navigation, then disruption of this region, using rTMS, will lead to a decrement in performance in navigating through the room to find a hidden object, but not in identifying what the object is (the control condition).

Primary outcome measure: As described just above, to determine baseline performance, we will also apply rTMS to the control vertex site, and predict a decrement in performance on the visually-guided navigation task, only after rTMS is applied to OPA (but not vertex). There are no secondary outcome measures.

5. Study Intervention/Investigational Agent

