During the second visit (the rTMS visit), participants will be seated comfortably in a chair and asked to complete either a simple computer-based task (e.g., imagine you are walking through the room, and respond via button press whether they can leave through a door on the left, center, or right wall, as indicated by a continuous path on the floor), or a simple behavioral task that will require them to actually walk around in a small room and search for hidden objects. Either during, or just before, each of these tasks, participants will receive rTMS. In rTMS, we place a small plastic coil next to the participant's head. The position of the coil will be guided by the fMRI study described just above, which was conducted on that participant in the prior visit. The coil will be placed over the relevant brain region using the Brainsight TMS-MRI co-registration system for visualizing the coil position with respect to the participant's individual fMRI scan. The coil will then generate a magnetic pulse, and stimulation will occur. During stimulation, the participants may feel a gentle flick, and hear an audible click. The pulse is not usually painful, but it can cause a twitch of the hand or face muscles. Even though hearing loss is a rare

Page 7 of 17 Version: Version 1 04/11/21

occurrence from rTMS, hearing protection (i.e., ear plugs) will be used during the TMS experiments.

Instead of having source records (i.e. surveys), we are only going to collect brain image data for the fMRI portion of the study and psychophysical data for the rTMS portion. No further data is collected after procedures are completed.

During the experiment, participants may withdraw at anytime. After the experiment, participants will remain under supervision for about 15 minutes, verbally confirm they feel safe to leave (after the 15 minutes), and then will be escorted to the exit. If participants do not feel safe to leave after the 15 minutes is up, they will be asked to stay until you do feel safe to leave. If further assistance is needed, [name] (M.D./Ph.D), the head of FERN, will be contacted to come to the testing room.

7. Data Specimen Banking

All participants will be given a non-identifying ID number. Hardcopy data will be kept in a locked filing cabinet in a secure office. Electronic data will be stored on a secure electronic hard drive. Electronic data will also be shared with Emory University and will be secured according to Emory IT policies.

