We plan to enroll about 38 healthy adult participants (19 for each of the two proposed experiments). The number of participants was determined using a power analysis, with an effect size of $\eta_P{}^2 = 0.14$ (estimated from previous similar studies), an alpha level of 0.05, and power at two levels: 90% and 80%. Thus in each of the two proposed studies, we will test 19 participants (90% power), but could lose 4 participants to attrition and still have 80% power. Note in prior TMS studies, a similar number of participants were tested.

We will recruit an equal number of men and women, and all efforts will be made to recruit minorities. No exclusion of women and minorities is necessary for this study. Census estimates from 2010 for Atlanta, Georgia, were 43.1% white, 50.1% African American, 0.2% American

Page 9 of 17 Version: Version 1 04/11/21

Indian and Alaskan Native, 2.7% Asian, and <1% Native Hawaiian and other Pacific Islander; Hispanic or Latino were 5.3%. Using these census estimates, we will recruit minority participants to ensure that the subject sample represents the community. Recruitment of women and minorities will be assessed quarterly to ensure adequate representation. Participants will be recruited via the subject pool database maintained by the Emory University Psychology Department.

13. Recruitment Methods

Participants will be recruited via the subject pool database maintained by the Emory University Psychology Department. The database involves names and contact information of people who have agreed to participate in research for course credit (1 credit up to 60 minutes) or to be paid for their participation. However, the participants in this study will not receive credit, but rather will be paid \$20/hour in cash for the rTMS portion. For the fMRI portion, the participants will be paid \$25/hour. Additionally, participants may be recruited in the community and at Emory University by word of mouth. No flyers or printed advertisements will be used.

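### Could object identification in the walking experiment look spared only because the OPA disruption has faded by the time it is measured?

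*Combined protocol and SAP*

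**What the plan says.** Section 4, hypothesis ii, predicts that disrupting OPA lowers performance "in navigating through the room to find a hidden object, but not in identifying what the object is (the control condition". The primary outcome measure printed beneath it is narrower. It compares OPA with the vertex control site and predicts a fall in navigation performance "only after rTMS is applied to OPA (but not vertex". It names no secondary outcomes.

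Section 6 describes the experiment as "a simple behavioral task that will require them to actually walk around in a small room and search for hidden objects" and does not mention the identification step. On timing it says: "Either during, or just before, each of these tasks, participants will receive rTMS".

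Two other sections bear on timing. Section 2 gives the aim as using rTMS to "temporarily disrupt the functioning of particular brain regions in healthy adults while we show them simple visual stimuli of places", and the same sentence goes on to the behavioural task, with walking round a small room as its example. Section 3 reports that in the cited face, scene and object recognition studies the disruption "occurred between ~50 to 150 ms after a briefly flashed stimulus, and after that all processing returned to normal", a window that it says "demonstrates that the effects of rTMS on visual cortex are very transient".

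Section 12 gives the size of each experiment: "we will test 19 participants (90% power), but could lose 4 participants to attrition and still have 80% power".

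**The concern.** Hypothesis ii is a dissociation: one ability should suffer and the other should not. The unaffected half tells us something about OPA only if identification is tested while OPA is disrupted about as much as it was during navigation. If rTMS is given before the task, and a participant first searches and then names what was found, identification comes later and under weaker disruption. An absent effect could then mean either that OPA plays no part in identification or that the stimulation had worn off.

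The vertex condition does not separate these two readings. It controls for stimulation site and carries the same delay to identification, so it cannot show whether the OPA effect was still present. The protocol also stresses that rTMS effects are brief, which makes silence about the timing of the control more noticeable. At stake is the specificity half of hypothesis ii.

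**Working it through.** **1. Do the timing statements conflict?** Set side by side, they mostly do not.

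| Section | What it addresses | Timing for the walking task |
|---|---|---|
| 2 | Purpose of rTMS in both tasks | Disruption while the task is done |
| 3 | Cited studies with flashed stimuli, in support of transience | None; a different kind of task |
| 4 | Contrast of OPA with vertex | None; the word *after* belongs to the site contrast |
| 6 | Delivery of rTMS | During, or shortly before, left open |

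One open choice remains, in section 6. Section 2 shows the intent.

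**2. Which ways of running the task produce the bias?**

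| Conduct | Navigation | Identification | Consequence |
|---|---|---|---|
| Pulses continue through identification | disrupted | disrupted | fair control |
| rTMS before, both measures at the same delay | disrupted | equally disrupted | fair control |
| rTMS before, effect lasts only the 50 to 150 ms of section 3 | not disrupted | not disrupted | null on navigation, no false dissociation |
| rTMS before, identification after the search, effect fades over about a search's length | disrupted | less disrupted | specificity claim weakened |

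Only the last row causes harm. Each of its three conditions is an assumption; the protocol states none of them.

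**3. The plan's own power figure.** Inputs from section 12: partial eta squared 0.14, alpha 0.05, n = 19 and n = 15 (19 − 4). Assumed, because not stated: two repeated measures (m = 2) with correlation ρ = 0.5.

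- f² = 0.14 / 0.86 = 0.1628, so f = 0.4035 and the paired effect is dz = 2f = 0.807.
- Noncentrality λ = f² · n · m / (1 − ρ): 0.1628 × 19 × 4 = 12.37 for n = 19, and 0.1628 × 15 × 4 = 9.77 for n = 15.
- Power from the noncentral F with 1 and n − 1 degrees of freedom: 0.914 at n = 19 and 0.828 at n = 15. These n are the smallest that reach 90% and 80%, so the stated figures reproduce.

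**4. How often would a real identification effect be missed?** Suppose OPA disruption truly harms identification as much as navigation, and a fraction r of that effect is left at measurement. Then λ becomes r² times the value above.

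| r | Power, n = 19 | Missed, n = 19 | Missed, n = 15 |
|---|---|---|---|
| 1 | 0.914 | 9% | 17% |
| 0.75 | 0.704 | 30% | 41% |
| 0.5 | 0.384 | 62% | 69% |
| 0.25 | 0.133 | 87% | 89% |

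The row r = 0.5 can be read in two ways: a full-sized effect that has half faded, or a half-sized effect with no fading. The miss rate is the same, so at this sample size a null on identification is weak evidence even under perfect timing.

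**5. Can r be pinned down?** No. With exponential fading of half-life h and a search of length T, r = 2^(−T/h). At an assumed h of 60 s, r is 0.84, 0.71 and 0.50 for searches of 15, 30 and 60 s, and identification is missed in 20%, 35% and 62% of studies of 19. The documents give neither T nor h for this task, so the answer is whatever those two inputs make it.

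**6. The primary comparison.** Fading can shrink a true OPA effect on navigation but cannot create one. Whether it would cost power depends on whether 0.14 stands for the effect at task onset or averaged over the task. Section 12 does not say; on the averaged reading, power stays at 0.914.

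**The case for a change.** The strongest case for acting is that identification is part of the hypothesis, yet it appears once and is never described as a procedure. The protocol points to no other document for it. Finding and then naming is the natural order of such a task. The vertex condition cannot reveal a faded effect, and a sentence stating the timing would cost almost nothing.

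The omission stands, and so does the point about vertex. Three things weaken the rest:

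- Natural order is not stated order, and section 6 expressly permits stimulation during the task, which removes the problem.
- The miss rates assume that OPA disruption harms object identification as much as navigation. Titles in the protocol's own reference list lean the other way: one calls OPA's role in scene perception selective, and another reports impaired scene categorization with object categorization unaffected. These are titles only, but they give no reason to take equal harm as the central case.
- The low cost of a clarifying sentence shows that it would be tidy, not that the plan is unsound without it. The more substantial remedy, separate identification trials at a matched delay, would take session time within a visit of about 90 minutes and would give up a control matched on walking and searching.

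**Conclusion.** This is missing operational detail, and no change to the plan follows. The protocol does not place the identification measure in time. A team that follows the intent in section 2, with disruption while the task is under way, or that takes both measures at the same delay, has a fair control. The harmful sequence depends on three conditions that the protocol does not state, and the brief window it does cite would produce a null on navigation, not a false dissociation. The stated primary outcome is not exposed to a false positive, and no secondary outcome depends on the control.

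The possible size cannot be fixed. Given an equal true effect and an assumed correlation of 0.5, the chance of missing an identification effect with 19 participants runs from 9% with no fading to 62% with half the effect gone. Since a half-sized effect without fading gives the same 62%, a null on identification should be read cautiously whatever the timing. If the two delays turn out to differ, that belongs in the interpretation of the result and does not alter the design.

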Participation will require up to two visits each taking about one and a half hours. During the first visit, participants will be scanned (using fMRI). Before scanning, all participants will be asked to remove all jewelry and other metal-containing objects (including credit cards). They will then enter a large room where a powerful magnet is located. They will be asked to lie down on a narrow table and will be put in a small tunnel approximately 6 feet long and 2 feet in diameter. They will then be asked to lie as still as possible during the scan for approximately 90 minutes. During scanning, they will hear a loud banging noise as the MRI machine takes pictures of their brain. As a consequence, they will be given earplugs to make them more comfortable. While they lie in the scanner, a computer display will be placed at one end of the tunnel. They will be able to see the display through the back-projecting mirror in front of their face. Once scanning begins, they will then need to respond to things they see on the display screen, and for this they will be given a small box with buttons that will be placed under their hand when they are placed into the scanner. Specifically, they will be asked to view pictures of faces, places, objects, and abstract patterns. Such "localizer" stimuli enable us to identify (or localize) the brain region (i.e., OPA) in each individual using fMRI that will then be targeted with rTMS in the proposed study.

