8. Sharing of Results with Participants

The research material obtained will consist only of brain images (MRI and fMRI), and psychophysical data (rTMS) that will be used solely for research purposes. We will not make use of any existing specimens or records. The data and subject identity will remain confidential. All participants will be identified by codes known only to the members of my research team. All paper data will be secured in a locked filing cabinet in a secure office in the Psychology Building at Emory University. All electronic data will be password protected and stored on a computer in the Psychology Building at Emory University, according to Emory IT policies.

Furthermore, the study team will review the MRI scan. If there are any incidental findings or we discover that data from the scan suggest something that may be important clinically, we will share them with [name], the head of FERN, who will determine its clinical relevance.

9. Study Timelines

Participation will require up to two visits. During the first visit, participants will be asked to lie as still as possible during the fMRI scan for approximately 90 minutes. During the second visit (the rTMS visit), participants will be seated comfortably in a chair and asked to complete either a simple computer-based task or a simple behavioral task that will require them to actually walk

Page 8 of 17 Version: Version 1 04/11/21

around in a small room and search for hidden objects. This will also take approximately 90 minutes.

Study enrollment will begin shortly after IRB approval and continue until all participants' data are collected (38 adults). Based on our prior experience with collecting TMS data in typical adults, we estimate that we can successfully complete the two proposed studies within two to three years.

10. Inclusion and Exclusion Criteria

Inclusion:

- i) Healthy adults aged 18 and up
- ii) Normal or corrected-to-normal vision

Exclusion:

- i) no metal in the body
- ii) personal or first-degree family history of epileptic seizure
- iii) a known brain injury
- iv) claustrophobia
- v) taking certain medications that may increase the risk of seizures (e.g., bupropion, varenicline, chlorpromazine, theophylline) or reduce the effects of rTMS, such as benzodiazapines
- vi) Adults unable to consent, pregnant women, prisoners

11. Vulnerable Populations

This research does not involve any individuals who are in the vulnerable populations list.

12. Local Number of Participants

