To ensure that the participant does not have any metal in his or her body, the study team administers a screening form (attached) to the participant both during recruitment and before going into the scanner. Furthermore, to minimize any possible risk of a seizure during testing, the participant will certify that neither she, nor parents, brothers or sisters, or children have ever suffered an epileptic seizure. The participant will also certify that she has never suffered a known brain injury, and that she is not taking certain medications that may increase the risk of seizures or reduce the effects of rTMS. To ensure that the participant does not have any of the above contraindications, the study team administers another screening form (attached) to the participant both during recruitment and before study participation.

14. Withdrawal of Participants

Some people become nervous or claustrophobic (anxious or afraid of closed spaces) in the fMRI scanner. If this happens to the participant, they may ask to be withdrawn immediately. They may also experience a sense of dizziness in the magnet. Such dizziness is due to the strong magnetic field, and if it disturbs them, they may ask to be withdrawn.

The most common risk and discomfort of rTMS expected in this study is mild discomfort or tingling due to twitching of muscles in the head or face. If, at any time, the participant feels uncomfortable due to such twitching, he or she may indicate so verbally, and we will stop the experiment. In the studies cited above between 5-15% of participants experience discomfort, and withdraw from the study.

The study team has the right to end the subject's participation in this study for any of the following reasons: If it would be dangerous for the participant to continue, if the participant does

Page 10 of 17 Version: Version 1 04/11/21

not follow study procedures as directed by the study team, or if the sponsor decides to end the study.

The subject's participation is voluntary, and she has the right to refuse to be in this study. The participant can stop at anytime after giving her consent. The participant has the right to leave a study at any time without penalty. The participant may refuse to do any procedures the she does not feel comfortable with, or answer any questions that she does not wish to answer. If the participant choose to withdraw, she can request that her information not be used in the study.

15. Risk to Participants

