With fMRI, the risks are minimal. For example, the MRI machine is loud (similar to riding in a loud train), and, as such, participants will be given earplugs to lessen the noise. Participants may experience some muscle discomfort while lying in the scanner. They may also become too hot or too cold, in which case they may ask for an adjustment of room temperature or a blanket. Some people become nervous or claustrophobic (anxious or afraid of closed spaces) in the scanner. If this happens to the participant, they may ask to be withdrawn immediately. They may also experience a sense of dizziness in the magnet. Such dizziness is due to the strong magnetic field, and if it disturbs them, they may ask to be withdrawn. Because the magnetic field will affect any metallic object, they should not participate if they have any type of metallic implant in their body, including pacemakers, aneurysm clips, shrapnel, metal fragments, orthopedic pins, screws, or plates, metallic IUD's, or piercings that you cannot remove. If potential participants have any of these items in their body, there is a risk that the magnetic field could cause them to move or heat up. It is important that they inform the study personnel if they have any implants. To ensure that the participant does not have any metal in his or her body, the study team administers a screening form (attached) to the participant both during recruitment and before going into the scanner.

This type of brain scan is not designed to detect problems of the brain. A radiologist will not be reading the scan. The study team will review the scan. If there are any incidental findings or we discover that data from the scan suggest something that may be important clinically, we will share them with [name] (M.D./Ph.D), who will determine its clinical relevance, and contact you with further information (e.g., to seek a health professional).

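### Does Section 10 exclude people who have no metal in the body, and does the plan need to change because of it?

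*Combined protocol and SAP*

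**What the plan says.** Section 10 has two lists. The exclusion list has six items, and the first reads "no metal in the body". The second reads "personal or first-degree family history of epileptic seizure". The other four cover known brain injury, claustrophobia, certain medications, and a group of people who may not enter (those unable to consent, pregnant women and prisoners).

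Three other sections mention metal:

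- **Section 13 (Recruitment Methods)** introduces a screening form with the purpose "To ensure that the participant does not have any metal in his or her body".
- **Section 15 (Risk to Participants)** names kinds of implant, fragment and fixed piercing, and says of people who have them that "they should not participate if they have any type of metallic implant in their body". It then gives the procedure: "the study team administers a screening form (attached) to the participant both during recruitment and before going into the scanner".
- **Section 6 (Procedures Involved)** says "During the first visit, participants will be scanned (using fMRI"), and that before the scan "all participants will be asked to remove all jewelry and other metal-containing objects".

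Section 12 (Local Number of Participants) gives the size of the group to which the criteria apply: "We plan to enroll about 38 healthy adult participants".

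**The concern.** An exclusion list works by naming what keeps a person out. Five of the six items do so. The first names the absence of something, so under its heading it keeps out those who have no metal and lets in those who do. That reverses Sections 13 and 15.

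The item deserves a second look because it is a safety criterion. The first visit is an MRI scan, and Section 15 warns that metal in the body could shift or grow hot in the magnetic field. Section 10 is the formal statement of who may enter, so one would expect it to agree with the screening and risk sections. If someone screened from Section 10 alone and took it at its word, a person with an implant could reach the scanner. A reader could also ask whether the other criteria were drafted with the same lack of care.

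**Working it through.** No arithmetic applies. The check is a comparison of wording, followed by a check on whether the wording governs anything that happens.

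**Step 1. Direction of each statement about metal in the body.**

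| Place | Literal effect on a person with metal | Literal effect on a person without metal |
|---|---|---|
| Section 10, exclusion item i | not excluded by this item | excluded |
| Section 13, purpose of the form | screened out | passes |
| Section 15, risk text | should not take part | may take part |

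Sections 13 and 15 agree. Section 10 item i stands alone.

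**Step 2. Is the literal reading a live one?** Apply Section 10 item i and Section 15 together. The first removes everyone without metal, and the second removes those with metallic implants. Almost nobody is left, yet Section 12 plans for about 38 participants and Section 24 calls that recruitment highly feasible. Item i could be followed in isolation, but not alongside the rest of the document. Read as a requirement for entry, it agrees with Sections 13 and 15 with no word altered. The error is therefore one of placement or negation.

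**Step 3. Does Section 6 add a further contradiction?** No. Its text is about jewelry, credit cards and similar articles taken off before the scan. These are outside the body. The sentence neither conflicts with item i nor guards against an implant, so it counts for nothing on either side.

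**Step 4. What decides entry in practice?** According to Section 13, the study team uses forms to establish that contraindications are absent. One covers metal, and another covers seizure history, brain injury and medication. Section 15 repeats the metal form and its timing: once during recruitment and once before the scanner. A person with metal would therefore have to pass the same question twice, on a form whose stated purpose is to find it.

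**Step 5. Does anything statistical depend on it?** Section 12 bases the sample size on an assumed effect size, alpha and power for 19 participants in each of two experiments (2 × 19 = 38). None of these inputs involves the metal criterion. The outcome measures in Section 4 do not involve it either.

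**The case for a change.** The best argument for acting is that the error is on the page, costs one line to correct, and sits in a safety criterion. The heading, the item and its neighbours are all intact, so neither redaction nor text extraction explains it. The revision table is empty, so this is current text. That every reader understands what was meant does not make the wording right, and an obvious intent makes the correction uncontroversial.

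All of that stands as a description of the slip. It does not show a consequence. Section 15 states the restriction more fully than Section 10 does, and the form turns it into a procedure carried out twice. Correcting item i would leave enrolment, procedures, sample size and analysis as they are.

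Two smaller points also remain. The screening forms are described as attached but are not in the public document, so their wording cannot be checked. The scope also differs a little: Sections 10 and 13 speak of metal in the body generally, while Section 15 lists implants, fragments and piercings that cannot be removed. That difference does not affect the direction of the criterion.

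**Conclusion.** The observation is correct: item i of the exclusion list is worded the wrong way round relative to its neighbours and to Sections 13 and 15. It is a clerical slip of the lowest weight, and correcting it would bring no gain in how the study is run or analysed. The expected effect on enrolment is negligible, and there is none on power or inference.

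This rests on two assumptions: that the metal form asks what Sections 13 and 15 say it is for, and that it is given at both of the stated times. The document gives no reason to doubt either. The line may be brought into agreement with Sections 13 and 15 as an editorial matter at any convenient revision, but the plan does not depend on it.
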